1.0 Background

1.1 Rationale for selected approach

The third-generation aromatase inhibitors (AIs) anastrozole, exemestane, and letrozole, all play a major role in the adjuvant therapy of postmenopausal women with early stage estrogen receptor α (ER α)-positive breast cancer^{1,2}. The assumption is that for all three AIs the mechanism of action in inhibiting tumor growth is only through decreasing estrogen production from androgenic precursors, by inhibiting aromatase³, which is encoded by the CYP19A1 gene⁴⁻⁶. Whereas all three AIs are potent in terms of inhibition of *in vivo* aromatization⁷⁻⁹, letrozole has been found to be the most potent¹⁰. However, large phase III adjuvant clinical trials do not indicate any difference in efficacy between the three AIs. Specifically, the MA.27 trial showed no significant difference between anastrozole and exemestane¹¹ in terms of DFS, and the FACE trial showed no difference between anastrozole and letrozole in terms of both DFS and OS¹².

We previously performed a pharmacokinetic and pharmacodynamic study in 649 patients receiving anastrozole adjuvant therapy¹³ that showed 21% and 30%, respectively, had estradiol (E2) and estrone (E1) concentrations above the lower limit of quantitation (LLQ), with a broad range of detectable concentrations.

Until recently there were no clinical studies which systematically tested whether the degree of estrogen suppression is associated with AI efficacy in early stage ER α -positive breast cancer. To address this unmet need, matched case-control studies¹⁴ were performed utilizing data from the MA.27 and PreFace trials. MA.27 enrolled postmenopausal women with resected stage I-III ER α -positive breast cancer who were randomized to either anastrozole or exemestane for five years. PreFace evaluated adjuvant letrozole in a single-arm phase IV trial. A breast event was considered to be any of the following: local-regional breast cancer recurrence [including ipsilateral DCIS], distant breast cancer recurrence, contralateral breast cancer [invasive or DCIS], or death with or from breast cancer without prior recurrence.

Due to the lack of an independent validation cohort, a bootstrap re-sampling approach was undertaken to determine ‘best’ cut points for the biomarkers, E1 and E2. Specifically, 500 bootstrap samples were constructed by sampling with replacement using 222 matched case-control sets from the 247 matched case-control sets. The set of potential cut-points assessed for each biomarker included values from its lower limit of quantification to its 85th percentile value (across all women). The ‘best’ cut point for a given biomarker was chosen using the maximum concordance approach of Liu.¹⁵ Specifically, for each potential cut point y_i , an indicator variable x_i was constructed where $x_i=1$ if the patient’s biomarker value was at or above y_i ; $x_i=0$ otherwise. Then, for each bootstrap sample, j , and each cut point, i , a concordance statistic C_{ij} was generated from fitting a stratified Cox model with case-control set as the strata, time set to the constant of 1, and the indicator variable for the cut point was fit to the data.¹⁶ The cut point where the maximum value of the concordance statistic, $\max C_j$, occurred was determined for each bootstrap sample j . The cut point most often found to be the $\max C_j$ cut point across the 500 samples was chosen for further evaluation. Having established cut points for E1 and E2, multivariate conditional logistic regression modeling using all 247 matched pairs was used to refine the model of risk. A secondary exploratory analysis was carried out using the refined model to obtain an estimate of the odds of EBCE for each treatment cohort separately. Statistical analyses were carried out using SAS 9.4 and the survConcordance() function in the survival package of R software.

The pre-AI E1 and E2 concentrations were similar among the 3 treatment cohorts, and were highly correlated within each treatment cohort with Spearman rank coefficients (ρ) of 0.84 for anastrozole; 0.89 for exemestane; and 0.90 for letrozole. After six months of AI therapy, E1 and E2 concentrations were below the LLQ in 41.3% and 11.9%, respectively, for anastrozole; 63.7% and 35.4%, respectively, for exemestane, and 79.3 % and 48.7%, respectively, for letrozole. The correlation between E1 and E2 concentrations after six months of AI therapy was moderate for anastrozole ($\rho= 0.54$) and exemestane ($\rho=0.52$) but weak for letrozole ($\rho= 0.15$). There was a very weak correlation between both E1 and E2 with AI concentrations after 6 months of treatment ($\rho=-0.20$ and -0.12 for anastrozole; -0.18 and -0.12 for exemestane, and -0.11 and -0.09 for letrozole, respectively). Six-month plasma concentrations of each of the AIs showed substantial inter-patient variability.

1.2 Estrone and Estradiol Suppression and Risk of an Early Breast Cancer Event

A potential cut point for E1 after six months of treatment was searched for between its lower limit of quantification (1.0 pg/mL) and the 85th percentile value of its distribution (1.7 pg/mL). For each cut point, a stratified Cox model was fit to the first of 500 bootstrap samples, and an estimate of the odds of EBCE and the concordance statistic was determined. This process was repeated for the remaining 499 bootstrap samples. From the 500 estimates of the odds ratio for a given cut point, the median and 2.5th and 97.5th percentile value of its distribution was determined and presented in Figure 1 for E1 and in Figure 2 for E2. The value of E1 most often having the maximum concordance value was 1.3 pg/mL and as such is the threshold for E1 (Figure 1). The process was repeated for E2 searching between the lower limit of quantification (0.3 pg/mL) and 85th percentile value of its pre-treatment distribution (0.7 pg/mL). The value of E2 most often having the maximum concordance value among the 500 bootstrap samples was 0.5pg/mL (Figure 2).

Using the cut point values identified for E1 and E2, multivariate conditional logistic modeling was used to assess whether or not the risk of EBCE differed with respect to whether E1 and E2 remain at or above its threshold after 6 months of treatment. Patients with E1 ≥ 1.3 pg/mL and E2 ≥ 0.5 pg/mL were found to have a 2.2 fold (95% CI: 1.42-3.47) increase in risk of an EBCE relative to patients with E1, E2, or both below these thresholds.

The question as to whether this relationship holds for each treatment group was determined. **The risk of an EBCE was increased 3.0 fold (sets=91: 95% CI: 1.56-5.76, p=0.001) for those with E1 and E2 values at or above their threshold after 6 months of anastrozole;** but not in those treated with exemestane (sets=95: 95% OR=1.66; CI: 0.82-3.33, p=0.16) or letrozole (sets=59: 95% OR=1.62; CI: 0.39-6.82, p=0.51).

In the case of anastrozole, an odds ratio of three means that a patient with an E2 and E1 at or above the thresholds had a three-fold risk of recurrence compared with a patient with the same matching factors (in this case: age, disease stage, BMI category, and adjuvant chemotherapy status) who had an E2 or E1 below the threshold.

[figure not shown]
Figure 1

Figure 1 Legend. Bootstrap Resampling for E1 Odds Ratio Distributions from (all 247 Case-Control Sets). $E1 \geq 1.3$ vs. < 1.3 Odds Ratio (95% CI): 1.75 (1.19, 2.55), $p=0.004$

[figure not shown]
Figure 2

Figure 2 Legend. Bootstrap Resampling for E2 Odds Ratio Distributions from (all 247 Case-Control Sets). $E2 \geq 0.5$ vs. < 0.5 Odds Ratio (95% CI): 1.44 (1.02, 2.03), $p=0.04$

1.3 Preclinical laboratory studies supporting a difference between anastrozole and exemestane and letrozole

Our preclinical data indicated that anastrozole, but not letrozole or exemestane, behaved in a fashion similar to E2. Anastrozole could activate ER α -dependent transcription (Figure 3), but the effect decreased with increasing concentrations. Additionally, in the presence of 100 nM anastrozole, we also observed time-dependent ER α degradation. Given that these data indicated that anastrozole but not exemestane or letrozole, had a mechanism of action in addition to inhibition of aromatase, and was a ligand for ER α , we performed radioligand binding assays (Figure 4), surface plasmon resonance (Figure 5), and nuclear magnetic resonance studies (Figure 6) that confirmed that, indeed anastrozole was a ligand for ER α .

Figure 3.

[figure not shown]

Figure 3 Legend: Estrogen response element-dependent luciferase assay in CYP19A1 CRISPR KO T47D cells treated with indicated concentrations of E2, anastrozole (Ana), letrozole (Let) or exemestane (Exe).

Figure 4.

[figure not shown]

Figure 4 Legend: Radioligand binding assays. [3H]-anastrozole binding with ER α protein. TB: total binding, NSB: non-specific binding, SB: specific binding.

[figure not shown]

Figure 5 Legend: ER α binding assays of anastrozole at different concentrations as indicated using a surface plasmon resonance biosensor. Comparisons among all four compounds at 2 μ M.

[figure not shown]

Figure 6 Legend: Anastrozole binding of ER α detected by nuclear magnetic resonance (NMR) spectroscopy. One-dimensional proton Carr-Purcell-Meiboom-Gill NMR spectroscopy of 120 μ M anastrozole in the absence (top, red) and presence (bottom, blue) of 3 μ M ER α protein. Spectra were normalized to each other using β -mercaptoethanol (β Me) signal shown in purple.

We then tested the effect of anastrozole on cell proliferation in the presence of estrogen levels below, at, and above the thresholds identified in the clinical studies described above. In vitro, E1 and E2 below 1.3 pg/mL and 0.5 pg/mL, respectively, had little effect on CYP19A1 KO T47D cell proliferation. Anastrozole, but neither letrozole nor exemestane, potentiated estrogen effects on cell proliferation when estrogen levels were above the thresholds, compared to estrogen alone, especially when both E1 and E2 were above the thresholds (Figure 7 A-C). Anastrozole, but neither letrozole nor exemestane, potentiated estrogen-induced ERE luciferase activity when estrogen levels were above the thresholds (Figure 7 D-F). These phenomena were also observed in an MCF7 cell line.

Figure 7.

[figure not shown]

Figure 7 Legend: Anastrozole potentiates estrogen's effects when estrogen levels are above the thresholds. A. Cell growth of CYP19A1 KO T47D cells in the presence of anastrozole (A) (27 ng/ml) plus indicated concentrations of estrone (E1) (0.13, 1.3, 2.6, and 26 pg/ml) and estradiol (E2) (0.1, 0.5, 2.5, and 25 pg/ml). B. Cell growth of CYP19A1 CRISPR KO T47D cells in the presence of letrozole (L) (215 ng/ml) plus estrone (E1) and estradiol (E2). C. Cell proliferation of CYP19A1 CRISPR KO T47D cells in the presence of exemestane (E) (10 ng/mL) plus estrone (E1) and estradiol (E2). D-F. Estrogen response element-dependent luciferase assay in CYP19A1 CRISPR KO T47D cells treated with indicated concentrations of E1 (0.13, 1.3, 2.6, and 26 pg/ml), E2 (0.1, 0.5, 2.5, and 25 pg/ml), or in combination with anastrozole (A) (27 ng/ml), letrozole (L) (215 ng/ml), and exemestane (E) (10 ng/mL). Error bars represent the SEM of 3 independent experiments. **p<0.01.

1.4 Trial Design

To evaluate the clinical impact of these findings, this clinical trial is designed to evaluate anastrozole in the adjuvant setting for patients with early stage ER α -positive breast cancer. Specifically, E1 and E2 levels will be assessed in patients who receive standard dose adjuvant anastrozole (1mg once daily). For patients who have inadequate suppression of E1 and E2 after 2 months of treatment, with levels above the thresholds of 1.3 pg/ml and 0.5 pg/ml respectively, the dose of anastrozole will be escalated to 10 mg once daily. E1 and E2 levels will be re-assessed after 2 months of treatment on 10 mg of anastrozole. E1 and E2 will be measured by a CLIA-approved liquid chromatography with tandem mass spectrometry (LC/MS/MS) in the Immunochemical Core Laboratory at Mayo Clinic. Details of the methodology have been published¹⁷⁻¹⁹. In addition, anastrozole and letrozole concentrations will be measured by [name], at Indiana University, a long-time collaborator, who has performed these assays in past studies²⁰. The main purpose of performing the AI assays is to ensure that the patients are taking the drug, but we are also interested in the steady state concentrations of anastrozole in the women who take the 10 mg daily dose.

The 10 mg dose of anastrozole has been previously compared with standard 1 mg dosing in patients with metastatic breast cancer²¹. There was no difference in clinical efficacy and toxicities were comparable. Regarding the cost of anastrozole therapy, the 1 mg dose

costs about \$2/day and the 10 mg dose costs roughly \$20/day, which translates to \$60/month and \$600/month, respectively. For patients who receive anastrozole at 10 mg per day for 8-10 weeks, patients will be advised to take letrozole, an FDA-approved agent, to complete their course of adjuvant endocrine therapy. After 8-10 weeks of letrozole, patients will have blood samples obtained for E1, E2, and letrozole concentrations. The rationale for this approach is that further research will be required before it is known if continuing anastrozole at 10 mg per day will provide long term benefit to patients.

1.41 Safety Run-in

At the request of the FDA, re-registration to the ANA10 treatment portion of the trial will be initially limited to a maximum of 6 patients. After 6 patients have re-registered, enrollment will temporarily halt. If two or more of these 6 patients develop a DLT (as specified in Section 7.0 of the protocol) within 28-35 days of starting ANA10, the study will remain closed to enrollment to allow the study team to review toxicity data thoroughly and make decisions regarding changes to the protocol. If at most one of these 6 patients develops a DLT within 28-35 days of starting ANA10, the FDA will be notified and re-registration will be reopened.

1.42 Adjustments to Eligibility in Response to the COVID-19 Pandemic

Due to the COVID-19 pandemic and late 2020 surge in cases, some patients have experienced delays in their surgical procedures and have been started on endocrine therapy preoperatively to bridge to the operating room. Typically the time on treatment is several weeks or up to 4 months. In response to this, the protocol has been amended to adapt to these circumstances, and allow patients who have received preoperative endocrine therapy to participate. Specifically, the half-life of anastrozole and letrozole is approximately 50 hours and exemestane is 24 hours; as such, these agents are cleared from the system after 5 half-lives. To this end, patients who received preoperative endocrine therapy with an aromatase inhibitor can participate if they have been off treatment for at least 4 weeks prior to registration. This will allow adequate elimination of the drug and baseline steady-state prior to study participation. Tamoxifen is much less commonly used in postmenopausal women as preoperative therapy. Due to its longer half-life of 5-7 days, patients who received preoperative tamoxifen can participate if they have been off treatment for at least 12 weeks prior to registration.

In alignment with these changes, prior receipt of an aromatase inhibitor or SERM (tamoxifen or raloxifene) for the prevention of breast cancer is allowed. In this setting, given these agents are typically administered for up to 5 years, a longer wash out of 6 months is preferred.

Additionally, there have been delays for post-operative Medical Oncology consultation; as such, the requirement to complete all cancer treatment within 60 days prior to registration has been removed. Specifically, patients must have completed treatment, but any time between that and registration is permissible.

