3.23 HER2 positive breast cancer as defined by

- HER2 IHC $\geq 3+$
- HER2/CEP17 ≥ 2.0
- HER2/CEP17 < 2.0 and average HER2 copy number of ≥ 6.0 signals/cell

3.24 Prior endocrine therapy for this breast cancer.
Exceptions:

- 1) Pre-operative aromatase therapy (anastrozole, letrozole, or exemestane) and last treatment was ≥ 4 weeks prior to registration
OR
- 2) Pre-operative tamoxifen therapy and last treatment was ≥ 12 weeks prior to registration

3.25 Currently receiving any of the following cancer-directed therapies:

- Radiation therapy
- Systemic therapy such as chemotherapy (standard or investigational)

3.26 Bisphosphonate therapy started < 4 weeks prior to registration.
NOTE: If patient is currently on bisphosphonate therapy she must be on stable dose for ≥ 4 weeks prior to registration.
Patients not currently taking bisphosphonates will be allowed to start bisphosphonate therapy after completion of anastrozole (1mg and 10 mg daily (if given)). Information regarding bisphosphonate therapy will be collected.

3.27 Current use of systemic or topical exogenous estrogen or progesterone (menopausal hormone replacement therapy [HRT]).

3.28 Prior ovarian function suppression (leuprolide, goserelin, etc.).

3.29a Inability to provide informed consent.

3.29b History of contralateral DCIS or invasive breast cancer.
NOTE: Exception allowed if

1. Patient did not receive adjuvant endocrine therapy
OR
2. Patient received adjuvant endocrine therapy but has been off treatment for at least 6 months prior to registration

3.29c Concurrent active malignancy or history of malignancy ≤ 3 years prior to registration.
NOTE: Exceptions allowed for successfully treated cervical carcinoma in situ, lobular carcinoma in situ of the breast, papillary thyroid cancer, or non-melanoma skin cancer.

3.29d Prior prevention therapy with an aromatase inhibitor or a SERM.
Exception: Therapy with a SERM (tamoxifen or raloxifene) is allowed if patient has been off treatment for ≥ 6 months prior to registration.

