4.0 Test Schedule

4.1 Test schedule for breast cancer

Tests and procedures	Active Monitoring Phase								
	≤14 days prior to registration	At end of Cycle 1 ¹	Re-registration	After ReReg and prior to Tx on C2D1 ²	Nurse call 2-4 weeks after starting ANA10	First 6 pts: once during Cycle 2 Days 28-35 ³	At end of Cycle 2 ⁴	30 days after last dose of ANA10	At end of Cycle 3
Window	±7 days			±7 days		±7 days	±3 days	+14 days	
History and exam ⁵	X	X		X ⁶					X
Height and weight ⁷	X	X					X ^R		X
Adverse event assessment, vital signs (BP, pulse), ECOG PS	X	X		X	X ⁸	X ^R	X ^R	X ^R	X
Hematology: CBC/differential	X	X ^R				X ^R	X ^R	X ^R	
Chemistries: alanine transaminase (ALT), aspartate transaminase (AST), total bilirubin	X	X ^R				X ^R	X ^R	X ^R	
Research blood specimens (see Section 14.0) ^R	X ^R	X ^{R9}					X ^R		X ^R
Medication Diary		X					X		X

Cycle = 56-70 days (8-10 weeks), R= Research funded

¹ Approximately 9 weeks after start of ANA1 ±7 days; or at discontinuation of ANA1 if that event occurs earlier than 8-10 weeks.

² Visit to obtain prescription after blood results are received.

³ One-time safety assessment for first six patients who re-register to ANA10

⁴ Approximately 9 weeks after start of ANA10 ±7 days; or at discontinuation of ANA10 if that event occurs earlier than 8-10 weeks. Must be prior to starting letrozole.

⁵ Physical exam is required at baseline. After baseline, physical exam may be performed at any time as clinically indicated, but is not required for protocol.

⁶ Nurse visit for ANA10 education (prior to starting ANA10)

⁷ Only weight needed after baseline

⁸ Call to assess/collect adverse events and verify patient is taking ANA10 and wants to continue (no vital signs or PS); Refill ANA10 by mail if needed

⁹ E1 and E2 results required prior to re-registration.

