7.3 Cycle 1 Anastrozole (ANA1)

7.31 Basics

A research blood sample must be drawn at baseline prior to treatment or patient is unevaluable and must be replaced.

All patients will be prescribed the FDA-approved dose of anastrozole at 1mg daily (standard adjuvant dose) for the first 8-10 weeks.

At the end of the first cycle, blood will be drawn for drug levels and E1 and E2 levels.

Patients should be encouraged to take their anastrozole in the morning each day EXCEPT the day of the blood draw when they should take their anastrozole after this sample has been drawn.

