16.5 Analysis Plan for Secondary Outcome and Translational Endpoint

Descriptive statistics will be used to describe the distribution of E1 and E2 concentrations following ANA10 and letrozole. The percent change in E1 and E2 concentrations from pre-AI levels will be determined and graphically depicted using spider plots.

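### The endocrine washouts run to registration and HRT is barred only if current, but the baseline E1/E2 sample may be drawn up to 14 days before registration

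*Combined protocol and SAP*

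**What the plan says.** - **Washout clock.** Section 1.42 admits women who had a pre-operative AI if they "can participate if they have been off treatment for at least 4 weeks prior to registration", and gives the purpose: "This will allow adequate elimination of the drug and baseline steady-state prior to study participation". Criterion 3.24 uses the same clock ("last treatment was ≥ 4 weeks prior to registration") and treats tamoxifen likewise: "Pre-operative tamoxifen therapy and last treatment was ≥ 12 weeks prior to registration".
- **HRT.** Exclusion 3.27 reads "Current use of systemic or topical exogenous estrogen or progesterone (menopausal hormone replacement therapy [HRT", with no off-treatment interval. Criteria 3.24, 3.29b and 3.29d, by contrast, carry intervals of 4 weeks to 6 months.
- **Timing of the baseline sample.** Table 4.1 marks the baseline research blood in the column headed "≤14 days prior to registration". Section 7.31 sets only an upper limit: "A research blood sample must be drawn at baseline prior to treatment or patient is unevaluable and must be replaced". The specimen table in 14.1 likewise asks only that it precede the first day of Cycle 1.
- **Use of the sample.** Section 16.5: "The percent change in E1 and E2 concentrations from pre-AI levels will be determined", to be shown in spider plots.

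**The concern.** The washout exists to give a clean starting value, yet its clock stops at registration and not at the blood draw that supplies the value. A draw early in the 4.1 window falls inside the period that 1.42 set aside for the baseline to settle.

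The HRT gap is the more direct one. Section 13.7 judges eligibility as of registration. A woman who is on HRT when the sample is taken, and stops before she registers, satisfies 3.27. Section 9.4 then prohibits menopausal hormone therapy on study, so her later samples are off HRT. The fall caused by stopping HRT would be counted as suppression by the study drug.

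The two errors run in opposite directions. A baseline still held down by an AI understates the percent reduction, and one raised by HRT overstates it. Nothing in the protocol would identify these women. Section 9.1 records concomitant medication only from the first day of study treatment, and no section asks for the last AI or HRT date.

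**Working it through.** **1. Does this reach the primary result?** Section 16.1 states 87% power for 29 adherent patients, rejecting at 12 or more, null 25%, alternative 50%. The exact binomial gives P(X ≥ 12 | n = 29, p = 0.50) = 0.8675, so the plan's figure reproduces; the type I error is P(X ≥ 12 | n = 29, p = 0.25) = 0.039. Success is defined by E1 and E2 thresholds on treatment, so the baseline value does not enter. The same is true of re-registration (3.32) and the feasibility rule (16.41).

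**2. Shortest gap from last dose to baseline draw as written.** Gap = washout to registration minus days from draw to registration (at most 14, table 4.1).

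| Exposure | Washout to registration | Shortest gap to draw |
|---|---|---|
| Pre-operative AI | 28 days | 28 − 14 = 14 days |
| Pre-operative tamoxifen | 84 days | 84 − 14 = 70 days |
| HRT | none stated | 0 days |

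The ±7 days that appears at the start of the window row in 4.1 is not used here. The row looks shifted in the text available, and footnote 1 gives ±7 days to the end-of-Cycle-1 visit.

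**3. Is the drug cleared by then?** Section 1.42 gives half-lives of 50 hours (anastrozole, letrozole), 24 hours (exemestane) and 5–7 days (tamoxifen), and treats the AIs as cleared after five half-lives. Residual fraction = 2^(−t/half-life).

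- Five half-lives at 50 hours: 250/24 = 10.4 days.
- Anastrozole or letrozole at 14 days: 336/50 = 6.72 half-lives, 0.95% left. At 28 days: 672/50 = 13.44 half-lives, 0.009% left.
- Exemestane at 14 days: 14 half-lives, 0.006% left.
- Tamoxifen at 70 days: 10 to 14 half-lives, at most 0.1% left.

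The clearance rule is met even at the earliest draw. What is halved, from 28 to 14 days, is the time 1.42 allows for a settled baseline.

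**4. Direction of the error.** Let R be the true fractional reduction and f the drawn baseline divided by the true untreated baseline. Apparent reduction = 1 − (1 − R)/f. It is below R when f < 1 (estrogen not yet recovered from an AI) and above R when f > 1 (HRT). The documents give neither f nor R.

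**5. Who contributes.** By 16.1, 160 × 0.20 = 32 women are expected to qualify for ANA10, and 32 − 3 = 29 to be evaluable. The summaries after ANA10 and letrozole rest on about that many. How many had a pre-operative AI or recent HRT is not stated.

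**The case against.** The case for leaving this alone has real force.

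- **Reach.** Percent change is named in none of the goals in 2.1 to 2.3; goal 2.25 asks for concentrations. One descriptive sentence in 16.5 and its plots are affected, with no test or decision attached. This stands.
- **A narrow corner for the AI.** To reach 14 days, a woman must take the AI almost until surgery, need no radiation or chemotherapy afterwards (3.13 requires these to be finished), register at about day 28, and be drawn on the earliest permitted day. The delays in post-operative consultation described in 1.42 lengthen the gap. This stands; the number of women could be zero.
- **An early draw is allowed, not required.** Sections 7.31 and 14.1 also permit a draw after registration, and 6.6 allows up to 21 days before treatment starts. This too stands, but it means the timing is stated in two ways, and neither is tied to the last dose.

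Several stronger readings are tempting and are not supported:

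- That residual drug contaminates the baseline. At 6.72 half-lives the plan's own clearance rule is satisfied.
- That only 14 − 10.4 = 3.6 days remain for estrogen to recover. This assumes recovery starts only once five half-lives have passed, which nothing in the documents says.
- That the percent change is wrong by a known amount. If a true 90% reduction is assumed, a baseline recovered to half would read as 1 − 0.1/0.5 = 80%, and one doubled by HRT as 1 − 0.1/2 = 95%. All these inputs are invented; the figures show direction only.
- That drawing after registration solves the problem. A woman who stops HRT the day before registration could be drawn the day after.

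**Conclusion.** The mismatch is in the text and is worth correcting as a minor, inexpensive improvement. As written, the value used as the pre-AI level can be drawn as little as 14 days after the last AI dose, against the 28 days chosen, or during HRT. The HRT half is the stronger, since the gap can be zero.

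The effect is confined to the descriptive percent change and spider plots in 16.5. A reader might infer that the trial's main conclusion is at risk; it is not, because the primary endpoint, re-registration and the feasibility rule rest on absolute on-treatment levels. No size of bias can be stated: the number of women is unknown, and the documents give no estrogen-recovery time course and no estrogen levels on HRT. The conclusion assumes that sites use the full window in table 4.1 and that eligibility is judged at registration, as 13.7 says.

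**What to change.** 1. Reword 3.24, and 1.42 to match, so that the existing 4-week and 12-week washouts are counted to the baseline E1/E2 sample.
2. Apply criterion 3.27 at the time of that sample. Whether to add an off-HRT interval, and how long, is for the sponsor to set.
3. Reconcile the timing of the baseline draw in 4.1 with 7.31 and 14.1. Moving the draw to after registration is optional; item 1 alone settles the AI and tamoxifen washouts.
4. Record the dates of last AI and last HRT use at baseline.
5. In 16.5, repeat the percent-change summary without women whose sample fell inside the stated washout or was taken on HRT.

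The cost is protocol wording, two dates on the baseline form and one extra summary; no extra tube is needed. A few women would be drawn later. If the draw is moved after registration, some may need an extra visit, because table 4.1 shows none between registration and the end of Cycle 1.
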